  # subject level Logistic regression likelihood
  for ( i in 1:N){
    y[i]~ dbern( p[i])
    log(p[i]) <- beta1[center[i]] + beta2*trt[i] + beta3*strata[i]
  }
  # center level model (center is a random effect with a normal distribution
  for (j in 1:J){
    beta1[j] ~ dnorm(beta1.hat, tau.beta1)
  }
  beta1.hat ~ dnorm( 0.0, 0.0001) #variance = 1/0.0001 = 10000
  tau.beta1 <- pow(sigma.beta1, -2)
  sigma.beta1 ~ dunif(0, 100)
  # non-informative prior for treatment and baseline risk effects
  beta2~dnorm( 0.0, 0.0001 ) #variance = 1/0.0001 = 10000
  beta3~dnorm( 0.0, 0.0001 ) #variance = 1/0.0001 = 10000

  #Average RR across baseline risk levels.
  logRR <- beta2
  RR <- exp(logRR)
}

```

The above WinBUGS model is a log-binomial regression model. Similar to robust Poisson regression, the log-binomial regression model will correctly estimate the log relative risk for treatment and correctly estimate the standard error for this treatment effect.⁵

Propensity Analysis of Primary Outcome using non-Randomized Cohort Data

The propensity scoring analysis plan for the non-randomized component in NEST will include the following:

- 1) Prior to analysis, the study statistician, primary clinical investigator, and the coordinating center investigator will select 25 to 50 baseline measures that are at least potentially related to the process of choosing between drain or lap. As such, this selection will not assume the choice depends on any one individual but is the result of many stakeholders participating in the decision.
- 2) Build a Random Forest (2000 trees) to select a subset of variables that are most highly associated with the choice of lap or drain. Use variable importance measures to determine most important.

⁵ Barros AJ, Hirakata VN, Alternative for logistic regression in cross-sectional studies: an empirical comparison of models that directly estimate the prevalence ratio, *BMC Medical Research Methodology*, (2003) Oct 20;3:21. Free text at: <http://www.ncbi.nlm.nih.gov/pmc/articles/PMC521200/>.

- 3) Using the subset of variables from step 2, build a logistic regression model that predicts initial treatment while accomplishing the following as much as possible:
 1. produces propensity score logit distributions within drain and lap groups that have means close to zero and very similar variances,
 2. with respect to drain and lap groups, produces small propensity score adjusted covariate differences for the overwhelming number of baseline measures identified as relevant (balances covariates among the groups).

The outcome data is not involved in the analysis at this time. Only after a final set of propensity scores are calculated will the outcome data be analyzed while adjusting for propensity scores.

- 1) Make a yes/no determination if step 3 above gives sufficient evidence that propensity score adjustment can balance relevant baseline covariates among the groups.
- 2) If a propensity model can be built using covariates that are understood to be related to the treatment selection process and the model produces propensity scores which balance baseline covariate distributions among the groups, then the primary outcome will be analyzed using a robust Poisson regression model that will include propensity score logits as a covariate.
- 3) If the robust Poisson regression model is fit in step 4, then the estimated risk and propensity score adjusted relative risk will be compared to the risk adjusted relative risk calculated using the randomized subject data.
- 4) An informal comparison of relative risk point estimates and confidence intervals will be used to assess the similarity of the two relative risk estimates.

Combined Analysis of Randomized and non-Randomized Cohorts

This work is solely exploratory and will only be completed if analysis of non-Randomized Cohort can be considered useful. If the risk adjusted relative risk estimates in the two cohorts are in the same direction, or the propensity adjusted relative risk among the non-randomized cohort is in the same direction as the risk adjusted relative risk estimate in the randomized cohort, then a random-effects meta-analysis will be used to estimate the overall relative risk. The following will be done to complete this meta-analysis:

- 1) Estimate the overall treatment effect on the log RR scale using a fixed effect model:

$$\log(RR)_F = \frac{\sum w_i [\log(RR)_i]}{\sum w_i},$$

where $w_i = 1 / v_i$ and v_i is the variance of the i^{th} estimate of $\log(RR)$.

2) Estimate the Q statistic, which can be used to test for heterogeneity of treatment effect:

$$Q = \sum w_i [\log(RR)_i - \log(RR)_F]^2.$$

3) Estimate the variance needed for a random effects model:

$$\sigma^2 = \max \left\{ 0, \frac{Q - (2 - 1)}{\sum w_i - (\sum w_i^2) / \sum w_i} \right\}.$$

4) Estimate the random effect weights:

$$\tilde{w}_i = \frac{1}{\sigma^2 + v_i}.$$

5) Estimate the overall random effect estimate of log(RR):

$$\log(RR)_R = \frac{\sum \tilde{w}_i [\log(RR)_i]}{\sum \tilde{w}_i}.$$

6) Estimate a 95% CI for the random effect estimate of the log(RR):

$$\log(RR)_R \pm \frac{1.96}{\sqrt{\sum \tilde{w}_i}}.$$

Estimates of baseline risk adjusted relative risk on the log scale and the standard errors will be estimated from the robust Poisson regression models. The variance for the estimated baseline risk adjusted relative risk on the log scale will equal the square of the standard error calculated from the sandwich estimator.

Statistical Appendix A: Exploratory Analysis for Statistician's benefit (will be completed only after all publication required analyses are completed.)

Interestingly, bootstrap analysis of a binary outcome using Poisson regression, when the outcome is a function of treatment, produces an empirical distribution of estimated relative risk on the log scale that is approximated by a normal distribution. Also, an empirical 95% confidence interval for the relative risk on the log scale calculated from these bootstrap samples will approximate a 95% confidence interval for the relative risk on the log scale calculated for a robust Poisson regression model.

For example, using simulated data containing a binary outcome which is a function of treatment and a two level strata variable, the following results occurred:

- The estimated $\log(\text{RR})$ using a robust Poisson regression model was -0.209, compared to the true value of -0.208.
- The 95% CI for the treatment effect on the $\log(\text{RR})$ scale using robust Poisson regression was -0.347 to -0.071.
- The estimated median bootstrap estimate of $\log(\text{RR})$ using Poisson regression was -0.209, based on 10000 bootstrap samples.
- The 95% CI for the treatment effect on the $\log(\text{RR})$ scale using the bootstrap estimates was -0.356 to -0.078.

Also, Figure 1 shows that the 10,000 bootstrap estimates of $\log(\text{RR})$ from the Poisson regression does approximate a normal distribution.

[figure not shown]

Figure 1

The program used to study the relation between robust Poisson regression and bootstrapped Poisson regression of a binary outcome is included in Statistical Appendix B.

Given the robust Poisson regression estimates of $\log(\text{RR})$ are approximately normal, Bayesian analysis of the primary outcome will also use the normal approximation approach of Spiegelhalter, Abrams, and Myles. Namely, the marginal likelihood for the treatment effect will be approximated by a normal distribution with mean equal to the robust Poisson regression estimated log relative risk and standard deviation equal to the sandwich estimate of the log relative risk standard error. The robust Poisson regression model used in this analysis will be the same as the model defined on page 17 and 18. The model will also adjust for center by including center as a fixed effect, if possible.

In addition to assuming the marginal likelihood of the treatment effect is approximated by a normal distribution, normal priors will be used as well. As a consequent, the posterior will be a normal distribution with mean equal to a weighted average of the prior mean and the maximum likelihood estimate of the log relative risk calculated from the data. The variance of the posterior will be the inverse of the sum of the precisions (1/variance).

Prior:
$$p(\theta) = N(\theta | \mu, \sigma^2), \text{ where } \theta = \log(\text{RR})$$

Likelihood:
$$p(\text{data} | \theta) = N(\hat{\beta}_{\text{trt}}, se_{\text{sand.}}^2)$$

$$\text{Posterior: } p(\theta|data) = N \left(\frac{\frac{\mu}{\sigma^2} + \frac{\hat{\beta}_{irt}}{se_{sand.}^2}}{\frac{1}{\sigma^2} + \frac{1}{se_{sand.}^2}}, \frac{1}{\frac{1}{\sigma^2} + \frac{1}{se_{sand.}^2}} \right)$$

As with the MCMC analysis using WinBUGS, three default priors will be used, skeptical, “non-informative”, and enthusiastic. All three prior-to-posterior analyses will include a plot of the prior, normally approximated likelihood, and posterior. Although the most complete inference from each of the above defined prior-to-posterior analyses are the posterior distributions, the posteriors will be summarized by calculating $\Pr(\theta \leq 0)$ for each. Also, the posterior distributions will be summarized by calculating equal-tail-area 95% credibility intervals for θ and for $RR = \exp(\theta)$. The purpose of analyzing the data using normal approximation methods in addition to the previously defined MCMC methods is to explore the sufficiency of the normal approximation approach for estimating posterior distributions of RR using the robust Poisson regression models. As such, comparisons of the posterior distributions for $\log(RR)$ and comparisons of 95% credibility intervals for $\log(RR)$ and RR will be made, as well as comparisons of $\Pr(\log(RR) \leq 0)$.

Statistical Appendix B: Example of Similarity Between 95% CI of Treatment Effect Using Robust Poisson Regression and Bootstrap Based 95% CI of Treatment Effect Using Poisson Regression.

```
#Next study the distribution of bootstrap estimates of log(RR):
seed.val1 <- 1234
n <- 75
trt.effect <- 0.1875
strat.effect <- 0.06
p.drain <- 0.8
reps2 <- 10000

set.seed(seed.val1)
p.drain1 <- p.drain
p.drain2 <- (1-strat.effect)*p.drain
p.lap1 <- (1-trt.effect)*p.drain1
p.lap2 <- (1-trt.effect)*p.drain2
True.RR <- p.lap1/p.drain1

strat <- c(rep(c(0,1),c(n,n)),rep(c(0,1),c(n,n)))
trt <- rep(c(0,1),c(2*n,2*n))
y <- c(rbinom(n,size=1, p=p.drain1),rbinom(n,size=1,
p=p.drain2),rbinom(n,size=1,p=p.lap1),rbinom(n,size=1,p=p.lap2))
id <- 1:length(y)
sim.dat <- data.frame(id,strat,trt,y)

#Fit the robust Poisson regression model on simulated data.
mod1 <- glm(formula = y ~ trt + strat, data=sim.dat, family=poisson)
mod1.sandwich <- coefest(mod1, vcov=sandwich)[2,c(1,2)]
mod1.sandwich.CI.lower <- mod1.sandwich[1]-1.96*mod1.sandwich[2]
mod1.sandwich.CI.upper <- mod1.sandwich[1]+1.96*mod1.sandwich[2]
mod1.test.result <- 1*((0 < mod1.sandwich.CI.lower) |
(mod1.sandwich.CI.upper < 0))
CI.diff <- mod1.sandwich.CI.upper - mod1.sandwich.CI.lower
#Construct vector of True RR, Model Estimate, and Sandwich based 95% CI
comparison.vector <- c(log(True.RR), mod1.sandwich[1],mod1.sandwich.CI.lower,
mod1.sandwich.CI.upper, mod1.sandwich[2], CI.diff)
names(comparison.vector) <- c("log(True RR)", "Model Estimate", "95% CI,
Lower", "95% CI, Upper", "SE.trt", "CI.diff")
comparison.vector

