To avoid bias in selecting the final regression model for the risk adjusted analyses of the nonrandomized patients, the baseline predictors will be determined before the logistic regression analyses are performed. Selection will be based on biologic plausibility, the results of our prior observational study, and univariate analyses of trial results. Likewise the baseline variables used in the final models for propensity scoring will be determined before any of these analyses are performed. Diagnosis & prognosis will be assessed using methods developed in our prior observational study. Nominal p values will be calculated for secondary outcomes without adjustment for multiple comparisons. Exploratory subgroup differences will be performed.

We plan to collect the same data for eligible, non-randomized infants (with consent) as for randomized infants. This will allow comparison of the patient characteristics and outcomes in the randomized and non-randomized cohorts and perhaps assess the external validity of our study findings (generalizability). As a secondary analysis, the risk adjusted relative risk will be determined in the randomized & preference groups and the value of combining these cohorts will be evaluated. This approach, known as a comprehensive cohort design, has been recommended in a recent meta-analysis for rare diseases or for evaluation of emergency therapies.¹⁰ Whether this approach is useful or not will be a secondary aim and these analyses will not affect the primary analysis of the randomized cohort.

Currently, there is unavoidable uncertainty about differences between the Bayley II and III outcomes. Based on Network GDB data available at this time, it appears that a Bayley III score <85 best approximates that of a Bayley II <70 which has been previously used by the Network in the definition of neurodevelopmental impairment. As this trial progresses, an increasing body of data will accumulate regarding the differences in

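### Propensity variables are picked only for their link to the choice of procedure, so prognostic severity measures can be left out of the score

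*SAP*

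**What the plan says.** The SAP section on propensity analysis of the nonrandomized cohort works in three steps.

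- Step 1: three named roles choose, before analysis, "25 to 50 baseline measures that are at least potentially related to the process of choosing between drain or lap".
- Step 2: "Build a Random Forest (2000 trees) to select a subset of variables that are most highly associated with the choice of lap or drain". The rule for the cut is "Use variable importance measures to determine most important"; no number to keep and no threshold is given.
- Step 3: a logistic model for treatment is built from the step 2 subset. It should, as far as possible, balance the great majority of the measures judged relevant.

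Outcomes are held back meanwhile: "The outcome data is not involved in the analysis at this time" and "Only after a final set of propensity scores are calculated will the outcome data be analyzed while adjusting for propensity scores". A yes/no judgement on balance follows. If it is favourable, a robust Poisson model is fitted with the propensity logit as a covariate, and the resulting relative risk is described as adjusted for both risk and propensity.

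The protocol, under Statistical Analyses, says of the companion risk-adjusted model that "Selection will be based on biologic plausibility, the results of our prior observational study, and univariate analyses of trial results", and then: "Likewise the baseline variables used in the final models for propensity scoring will be determined before any of these analyses are performed".

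**The concern.** A propensity score removes confounding only for what it contains or happens to balance. The variables that must be in it are those that predict the outcome and also differ between the groups. The SAP's rule looks only at the link to treatment choice. It therefore ranks a strongly prognostic measure with a modest link to choice below a measure that drives choice strongly and matters little for outcome.

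The likely direction of any remaining confounding is known. The protocol's section on the comprehensive cohort design expects nonrandomized infants given drains to be at higher risk. Uncontrolled severity would thus favour laparotomy, which is the trial's own hypothesis. The estimate is one of two checks under Secondary Specific Aim 1, the other being conventional risk adjustment. Under the protocol's section on propensity scoring, a result favouring the same procedure as the randomized result supports generalizability. In the SAP's combined analysis, agreement in direction can trigger pooling of the two cohorts.

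**Working it through.** The plan gives no sample size, power or error rate for this analysis and does not state the size of the nonrandomized cohort, so there is no figure of its own to reproduce.

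**Can a prognostic variable be lost?** Take platelet count. It is on the protocol's list of baseline severity measures but is not one of the seven inputs to the risk formula (birth weight, gestational age, vasopressors, high-frequency ventilation, pH, FiO₂, preoperative diagnosis).

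- It enters step 1 only if judged related to the choice.
- It survives step 2 only if it ranks high for the choice, with an unstated cut.
- If dropped, step 3 cannot use it.
- The balance aim tolerates a few unbalanced measures and has no numeric limit.
- A negative balance judgement leads to no outcome model, not to restoring the variable.
- The risk covariate is coded low/high where the SAP defines its models, and platelet count is not part of it.

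So the answer is yes, although the text does not make it certain.

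**How much could it matter?** All inputs here are assumed: true log RR 0; 30 candidates, 21 of them noise; outcome model with propensity logit and a two-level risk covariate. Negative values favour laparotomy.

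- Design A: n = 200; 4 choice-only variables (treatment logit coefficient 0.9); 5 confounders (0.35 for treatment, 0.5 for outcome); 300-tree forest, top 8 kept; 250 cohorts.
- Design B: n = 150; 3 choice-only variables (0.8); 3 confounders strongly tied to choice (0.5; outcome 0.4); 3 weakly tied but more prognostic (0.25; outcome 0.6); about 72% events; 2000-tree forest, top 6 or top 10 kept; 100 cohorts.
- Design C: as A, but ranked by mean difference instead of a forest, with the strengths varied; 400 cohorts.

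| Design | Kept by the selection | Selected score, mean log RR (SD) | Confounder score, mean log RR (SD) |
|---|---|---|---|
| A | 4.0 of 4 choice-only; 2.0 of 5 confounders | -0.040 (0.113) | -0.006 (0.090) |
| B, top 6 | 88% choice-only; 53% strong; 17% weak-link prognostic | -0.061 (0.120) | -0.013 (0.105) |
| B, top 10 | 95%; 71%; 37% | -0.038 (0.126) | -0.013 (0.105) |
| C, choice-only 0.9, confounders 0.35 | 2.1 of 5 confounders | -0.044 | – |
| C, both 0.5 | 3.7 of 5 | -0.016 | – |
| C, choice-only 0.35, confounders 0.9 | 4.9 of 5 | -0.003 | – |

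Design B repeated with t-statistic ranking for n = 100 to 300 (400 cohorts each) gave -0.021 to -0.065 with the selected score and -0.007 to 0.001 with the confounder score. The SD was larger with the selected score in every one of those runs.

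Scale:

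- The hypothesised effect is log(0.65/0.80) = log 0.8125 = -0.208. The biases in B are 0.061/0.208 = 29% and 0.038/0.208 = 18% of it; the smallest in C is 0.003/0.208 = 1.4%.
- Risk adjustment alone in B gave -0.104. The selected score leaves 0.061/0.104 = 59% or 0.038/0.104 = 37% of that; the confounder score leaves 0.013/0.104 = 13%, and that remainder is little more than one Monte Carlo standard error (0.105/√100 = 0.011).
- Variance ratios: A (0.113/0.090)² = 1.58; B (0.120/0.105)² = 1.31 and (0.126/0.105)² = 1.44; C with equal strengths, about 1.2.
- Chance that the estimate favours laparotomy with no true effect, Φ(bias/SD): B, Φ(0.061/0.120) = 69% and Φ(0.038/0.126) = 62%; A, Φ(0.040/0.113) = 64%. With the confounder score: Φ(0.013/0.105) = 55% and Φ(0.006/0.090) = 53%.

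**Would the balance check catch it?** In B, 76% (top 6) or 71% (top 10) of the dropped weak-link prognostic variables had an adjusted standardized difference above 0.1, and 50% or 46% above 0.2. A check would often flag them. But with 75 per group the standard error of a standardized difference is about √(1/75 + 1/75) = 0.163, so even a truly balanced variable left out of the score exceeds 0.1 about 54% of the time (2 × [1 − Φ(0.1/0.163)]). A loose check cannot separate the breaches that matter from those that do not.

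**Timing.** The protocol has the variables of the final propensity models settled before these analyses. The SAP settles only the candidate list beforehand; the final variables come from the cohort's treatment data. If the protocol means all propensity work, the two differ. If it means the outcome analyses, the SAP complies.

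**The case against.** The strongest reply is that the size of the problem is assumed. The protocol names severity of illness first among the reasons drained infants may be at higher risk. If severity drives the choice strongly, the forest will keep it: with confounders at 0.9, 4.9 of 5 were kept and the bias was -0.003. In every scenario compared, the selected score was less biased than risk adjustment alone (design C: -0.062, -0.096 and -0.159, in table order). Both facts stand. A reader might infer that the rule does drop prognostic confounders; the documents support only that it can.

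The safeguards are also real. Balance is judged beyond the retained subset, a decision precedes any outcome model, outcomes stay out until the scores are final, and baseline risk is adjusted for. They are incomplete for the reasons in the working.

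A reader might also infer that surgeon or site preference and time of day are pure determinants of choice that should be removed. The documents do not support this. The protocol lists time of day among the reasons for higher risk in drained infants, and center is a randomization stratum and a model covariate. They identify no variable related to choice alone.

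Nor do they establish a flat contradiction between SAP and protocol. The word that opens the protocol's propensity sentence ties it to a model whose predictors may be chosen partly from univariate trial results, so settling variables beforehand there does not exclude looking at data.

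**Conclusion.** The point holds as a gap in the selection rule. Prognosis is not a criterion at any step, a dropped variable has no stated route back, and the safeguards do not guarantee control. Under the assumed inputs the residual bias in log RR ran from about 0.00 to about -0.06 (one run with t-statistic ranking reached -0.065), in most scenarios with a wider spread. These figures depend on the assumed coefficients, cut-offs and cohort size, and the simulations did not apply the go/no-go decision. They show how the rule behaves and do not estimate this cohort's bias.

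Consequences are limited. The protocol says the cohort analyses do not affect the primary analysis, the comparison of relative risks is informal, and pooling is exploratory. A reader might conclude that the trial's test of generalizability fails; that goes too far, because the propensity estimate is paired with conventional risk adjustment. What remains is a modest risk of apparent corroboration in the expected direction, avoidable at almost no cost.

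**What to change.** Amend steps 1 to 3 of the SAP's propensity section:

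- Before analysis, list the baseline variables expected to predict death or NDI: at least the seven risk-formula inputs in their original form rather than as the low/high stratum, plus blood pressure, platelet count and ventilator settings from the protocol's baseline data.
- Force these into the propensity model whatever their forest importance. Use the forest only to add variables, and state how many or by what threshold.
- Require balance on every forced variable against a stated numeric limit, chosen with the cohort's size in mind, and make the yes/no decision on that basis.
- Reconcile the text with the protocol by saying which variables are fixed before which analyses.

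Do not require removal of variables such as time of day or center.

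The cost is SAP wording and a few more terms in the propensity model. The named variables are already on the protocol's baseline list, and outcomes still stay out until the scores are final.

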In the proposed study, we will use risk adjusted relative risk to assess whether the results for randomized patients are generalizable to nonrandomized patients. If the findings for randomized and nonrandomized patients favor the same surgical therapy (as we would expect from the findings noted above for comprehensive cohort studies), we would presume the results are generalizable to the nonrandomized patients. If the findings are different, we could not be certain whether the difference resulted from chance, true differences in effectiveness for randomized and nonrandomized patients, residual confounding that could not be adequately adjusted in the analysis, or other reasons. However, the last reason would be most likely if as in prior studies, nonrandomized patients treated with drains are at systematically higher risk than those treated with laparotomy (due to severity of illness, time of day, or other factors). Such risk factors may be quite difficult to adequately assess.

The analytic approach noted above is a different and more conservative analytic plan compared to a true comprehensive cohort study. However our trial provides an excellent opportunity for the Network to explore whether analysis conducted as if our trial used a comprehensive cohort design would provide similar results as for a conventional randomized trial in a setting where there is considerable effort to minimize bias.

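### The propensity model is to be built toward near-zero mean logits in both groups, a target that weakens the score and rewards leaving out strong confounders

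*SAP*

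**What the plan says.** The SAP section on propensity analysis of the nonrandomized cohort works in stages.

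- Step 1: before analysis, the team "will select 25 to 50 baseline measures that are at least potentially related to the process of choosing between drain or lap".
- Step 2: a random forest is used to "select a subset of variables that are most highly associated with the choice of lap or drain".
- Step 3: from that subset, the analyst is to "build a logistic regression model that predicts initial treatment while accomplishing the following as much as possible". Two aims follow. Criterion 1 is that the model "produces propensity score logit distributions within drain and lap groups that have means close to zero and very similar variances". Criterion 2 is that it "produces small propensity score adjusted covariate differences for the overwhelming number of baseline measures identified as relevant".
- Next, without outcome data: "Make a yes/no determination if step 3 above gives sufficient evidence that propensity score adjustment can balance relevant baseline covariates among the groups".
- If the answer is yes, the logit enters a robust Poisson model as a covariate. The result, described as adjusted for both risk and propensity score, is compared informally with the randomized estimate.

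No tolerance is given for the near-zero means, for a small covariate difference, or for how many measures must balance. Criterion 1 concerns the logits themselves, not a difference that remains after adjustment.

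The SAP's overall design section says the scores are there to adjust for selection bias. The protocol's comprehensive cohort section discusses residual confounding for the case that, as in earlier studies, "nonrandomized patients treated with drains are at systematically higher risk than those treated with laparotomy".

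**The concern.** A propensity score that captures how the operation was chosen must, on average, be higher among infants who had laparotomy than among those who had drainage. A goal of near-zero means in both groups asks for that separation to disappear. This conflicts with the stem of step 3 (predict treatment), with step 2 (keep the strongest predictors of treatment) and with the purpose of the score. An analyst choosing between candidate models would find that criterion 1 favors the one without the variables that separate the groups most. If those variables also drive death or NDI, they are the confounders.

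If drained infants are the sicker ones, confounding left in the estimate makes laparotomy look better. The protocol would presume generalizability when both cohorts favor the same operation, and the SAP lets a same-direction propensity-adjusted relative risk open the pooled analysis. A weakened score could therefore produce false agreement if the trial favors laparotomy, or false disagreement if it does not.

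**Working it through.** The documents attach no figure to criterion 1, so there is none to reproduce. The check has three parts.

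**1. Exact property of the fitted model.** Let T = 1 for laparotomy and 0 for drain, L the fitted logit, e the fitted probability and p the share with laparotomy. Maximum likelihood with an intercept gives sum(T − e) = 0 and sum L(T − e) = 0. Hence Cov(L, T) = Cov(L, e). Since Cov(L, T) = p(1 − p) × [mean L in lap − mean L in drain],

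mean L (lap) − mean L (drain) = Cov(L, e) / [p(1 − p)].

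Because e rises with L, the right side is positive unless L is constant. In simulated fits the identity held to within 3e-15.

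The common value of a constant score is log[p/(1 − p)]:

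- 50:50 (the equal use assumed in the protocol's sample size section): 0
- 40:60: log(0.4/0.6) = −0.405
- 30:70: log(0.3/0.7) = −0.847

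So zero is the right center only at 50:50.

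**2. How near zero corresponds to how weak a score.** Assume normal logits with equal variance s² in the two groups and a 50:50 split. Then the gap equals s², the means are ±s²/2, and AUC = Φ(s/√2). It follows that the means are ±z(AUC)².

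| AUC | z(AUC) | Group means, ±z² |
|---|---|---|
| 0.60 | 0.2533 | ±0.064 |
| 0.75 | 0.6745 | ±0.455 |
| 0.80 | 0.8416 | ±0.708 |

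In the other direction, means of ±0.05 imply AUC 0.59, ±0.10 imply 0.62, ±0.25 imply 0.69 and ±0.50 imply 0.76.

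**3. Whether criterion 2 blocks the problem.** This is a simulation on assumptions that are not in the documents: 30 covariates, of which 2 are strong and 6 weak confounders; a 50:50 split; a true relative risk of 0.8125 (the SAP's planning value, 0.65/0.80); the logit as a covariate in Poisson regression; and no risk stratum in the outcome model.

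| n | Model | Mean logit, lap / drain | AUC | Covariates balanced | Top two, SD apart | Adjusted RR |
|---|---|---|---|---|---|---|
| 150 | all 8 confounders | 0.80 / −0.80 | 0.808 | 86% | 0.02 | 0.811 |
| 150 | two strongest dropped | 0.22 / −0.21 | 0.672 | 83% | 0.64 | 0.705 |
| 300 | all 8 | 0.71 / −0.72 | 0.798 | 95% | 0.01 | 0.809 |
| 300 | two strongest dropped | 0.16 / −0.16 | 0.652 | 91% | 0.64 | 0.702 |
| 20,000 | all 8 | 0.62 / −0.63 | 0.785 | 100% | 0.00 | 0.805 |
| 20,000 | two strongest dropped | 0.11 / −0.12 | 0.632 | 93% | 0.64 | 0.700 |

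Balanced means an adjusted difference within 0.1 SD at n = 20,000 and within 0.25 SD at the smaller sizes. The crude relative risk was 0.684 to 0.686.

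Dropping the two strongest confounders satisfies criterion 1 better and costs only 3 to 7 percentage points in the share of balanced covariates. It also moves the estimate from close to the true value to close to the crude one.

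**The case against.** The strongest reply is that criterion 1 is one of two building aims and does not appear in the decision to proceed. That decision rests on covariate balance, step 3 starts from the strongest predictors of treatment, and a review of balance should show two confounders 0.64 SD apart. The outcome model is also described as risk adjusted, and the high/low stratum is built from seven severity and diagnosis variables, so part of the confounding is handled outside the score. All of this stands and limits the harm. It does not remove it: criterion 2 tolerates exceptions, the yes/no decision has no threshold, and the plan still instructs the analyst to pull in the wrong direction.

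A reader might infer several stronger claims that the documents do not support.

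- *Only a score that cannot predict treatment would pass.* That is exact only at zero. The SAP asks for near zero, as far as possible, with no tolerance, so a score with AUC of about 0.6 to 0.7 might well be accepted.
- *An intercept-only score would be the plan's preferred model.* It sits at zero only with a 50:50 split, ignores the instruction to predict treatment, and should fail both criterion 2 and the balance decision.
- *The protocol predicts that drained infants in this cohort will be sicker.* The statement is conditional on the pattern of earlier studies recurring.
- *Generalizability hangs on this estimate.* It is one of two checks; the conventional risk-adjusted relative risk is the other. The protocol also concedes that disagreement could reflect confounding the score failed to remove.
- *Step 2 loses outcome predictors because it screens on treatment alone.* Criterion 2 most naturally covers the step 1 list, so a variable screened out of the model would still be checked for balance.

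**Conclusion.** The point holds as a flaw in a model-building rule. Near-zero mean logits in both groups cannot be pursued without weakening the score's prediction of treatment. This follows from the logistic score equations and needs no assumption about this cohort. The AUC figures assume normal logits of equal variance and a 50:50 split. The shift in relative risk from about 0.81 to 0.70 is an illustration only: it depends on assumed confounder strengths and omits the risk stratum, so the bias in the planned analysis could be smaller.

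The reach is limited to the secondary propensity-adjusted relative risk in the nonrandomized cohort and to the direction check that opens the exploratory pooled analysis. The primary analysis of randomized infants is unaffected. The rule should still be changed, because gaining experience with propensity scoring is a stated trial objective and the correction is a matter of wording.

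**What to change.** In step 3, delete the near-zero mean as a model-building goal. Select the model on propensity-adjusted standardized differences for all the covariates listed in step 1, against a stated threshold, and use the same threshold in the yes/no decision. A value of 0.1 is one example. A looser one may suit the cohort size: in the simulation at n = 150, even the model with every confounder left only 86% of covariates within 0.25 SD.

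Report the overlap and variance of the logits by group, but only as a diagnostic of whether covariate adjustment is credible. Overlap must not replace the mean as a quantity to optimize, since a constant score maximizes it. Forcing the seven risk-formula variables into the model is an option but is not needed to repair this point.

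The cost is SAP wording and a greater chance that the yes/no decision says the propensity analysis should not be run.
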